3.6.3 Statistical Methods for Safety Analyses

Safety and tolerability will be assessed by clinical review of all relevant parameters including AEs and outcomes of pregnancies.

The analysis of safety results will follow a tiered approach (Table 1). The tiers differ with respect to the analyses that will be performed. Safety parameters or adverse events of special interest that are identified *a priori* constitute “Tier 1” safety endpoints that will be subject to inferential testing for statistical significance with p-values and 95% confidence intervals provided for between-group comparisons. Other safety parameters will be considered Tier 2 or Tier 3. Tier 2 parameters will be assessed via point estimates with 95% confidence intervals provided for V160 dose regimen versus placebo comparisons; only point estimates by treatment group are provided for Tier 3 safety parameters. Safety results will be summarized for each vaccination dose and across all three vaccination doses.

There were no SAEs nor vaccine-type viral shedding (which is an event of interest for V160) observed in the V160 Phase I study. While vaccine-type viral shedding is an event of interest that can occur only in V160-vaccinated subjects, barring false-positive tests in placebo recipients, the 0% incidence of vaccine-type viral shedding observed in the Phase I study provides no informed, data-driven, non-zero incidence level around which a safety hypothesis can be formulated and tested. Therefore, there is no *a priori* identified AE or ECI for which a test of hypothesis will be conducted. Thus, no Tier 1 event is identified in this study. Categories of events considered as Tier 2 and Tier 3 in this study are shown in Table 1. In addition, AEs observed in at least 7 participants (representing 1% of N=700 participants per group) in any vaccination group will be categorized as a Tier 2 event. Incidences of the categories of events identified in Table 1 will be reported as percentages, generally calculated as $100\% \times (\text{number of participants who experienced the event} / \text{total number of participants with safety follow-up})$, except for outcomes of pregnancies, SAEs throughout the study duration, and vaccine-type viral shedding. The 95% CIs will be provided for vaccine versus placebo percentage point differences (percent in V160 dose regimen group minus percent in placebo) will be calculated using the Miettinen and Nurminen method [2], an unconditional, asymptotic method. No stratification factor will be used in the calculation of 95% CI.

Percentages of outcomes of pregnancies will be generally calculated as $100\% \times (\text{total number of specific pregnancy outcome being reported} / \text{total number of all relevant pregnancy outcomes})$. For example, the percent associated with the pregnancy outcome of *live births* will be calculated as $100\% \times (\text{total number of live births} / \text{total number of fetuses/infants with known outcomes})$. The numerator and denominator account for pregnancies with multiple fetuses (ie, twins, triplets, etc.) and do not treat such occurrences as a single pregnancy outcome or event. Further details will be provided in the sSAP that will be written for this study.

Vaccine-type viral shedding will be assessed in V160-vaccinated participants. In addition to the analysis strategy shown in Table 1, point and corresponding 95% CI estimates of incidence of vaccine-type viral shedding (number of participants observed with vaccine-type viral shedding/total person-years of follow-up) will be calculated separately for the V160 3-dose, V160 2-dose, and placebo arms. No treatment group comparisons (V160 vs. placebo or V160

3-dose vs. 2-dose arms) of the percent of participants detected with vaccine-type viral shedding will be conducted.

Summaries of SAEs (throughout the study duration) by system organ class will be provided as incidence rates (number of participants [or infants] observed with a specific SAE/total person-years of follow-up) rather than percentages.

Table 1 Analysis Strategy for Safety Parameters

| Safety Tier | Safety Endpoint | p-value | 95% CI for Comparison of V160 to Placebo | Descriptive Statistics |
|--------------------------------------------------------------------------------------------------------------------------------------------------------------------------------------------------------------------------------------------------------------------------------------------------------------------------------------------------------------------------------|-------------------------------------------------------------------------------|---------|------------------------------------------|------------------------|
| Tier 2 | Solicited injection site AEs ^a | | X | X |
| | Solicited systemic AEs | | X | X |
| | Vaccine-related systemic AEs | | X | X |
| | Any serious AEs (in study participants or infants born to study participants) | | X | X ^b |
| | Vaccine-related serious AEs within Days 1 through 14 after vaccination | | X | X |
| | Discontinuations due to AEs | | X | X |
| | Elevated temperature ^c | | X | X |
| | AEs by SOC observed in ≥7 participants in at least one vaccination group | | X | X |
| Tier 3 | AEs by SOC | | | X |
| | Outcomes of pregnancies | | | X |
| | Vaccine-type viral shedding | | | X [‡] |
| ^a All injection site AEs are considered vaccine-related. ^b Incidence rates (cases/total person-years follow-up) will be provided instead of percentages. ^c Defined as ≥38.0°C [≥100.4°] oral or equivalent AE = Adverse event; CI = Confidence interval; SOC = System organ class; X = indicated summary statistic will be provided. | | | | |

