9.3 Adverse Events (AE), Serious Adverse Events (SAE) and Other Reportable Safety Events

The definitions of an adverse event (AE) or serious adverse event (SAE), as well as the method of recording, evaluating, and assessing causality of AE and SAE and the procedures for completing and transmitting AE, SAE and other reportable safety event reports can be found in Appendix 4.

AE, SAEs, and other reportable safety events will be reported by the participant (or, when appropriate, by a caregiver, surrogate, or the participant's legally authorized representative).

The investigator, who is a qualified physician, and any designees are responsible for detecting, assessing, documenting, and reporting events that meet the definition of an AE or SAE as well as other reportable safety events. Investigators remain responsible for following up AE, SAEs and other reportable safety events for outcome according to Section 9.3.3.

9.3.1 Time Period and Frequency for Collecting AE, SAE and Other Reportable Safety Event Information

All AEs, SAEs and other reportable safety events that occur after the consent form is signed but before allocation/randomization must be reported by the investigator if they cause the participant to be excluded from the trial, or are the result of a protocol-specified intervention, including but not limited to washout or discontinuation of usual therapy, diet, placebo treatment or a procedure.

From the time of allocation/randomization through 14 days following the first vaccination(s) and from the time of any subsequent vaccination(s) through 14 days thereafter, all AEs, SAEs and other reportable safety events must be reported by the investigator. SAEs (regardless of causality), other reportable safety events (ie, Cancer, Overdose, pregnancy, and infant SAEs) are reportable throughout the duration of an individual's study participation. Exposure during breast feeding is reportable from Day 1 through Month 7.

Additionally, any SAE brought to the attention of an investigator at any time outside of the time period specified in the previous paragraph also must be reported immediately to the Sponsor if the event is either:

1. A death that occurs prior to the participant completing the trial, but outside the time period specified in the previous paragraph.

or

2. A serious adverse event that is considered by an investigator who is a qualified physician to be vaccine related.

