Investigators are not obligated to actively seek AE or SAE or other reportable safety events in former study participants. However, if the investigator learns of any SAE, including a death, at any time after a participant has been discharged from the study, and he/she considers the event to be reasonably related to the study treatment or study participation, the investigator must promptly notify the sponsor.

All initial and follow-up AEs, SAEs and other reportable safety events will be recorded and reported to the sponsor or designee within the timeframes as indicated in [Table 4](#).

Table 4 Reporting Time Periods and Timeframes for Adverse Events and Other Reportable Safety Events

| Type of Event | Reporting Time Period: Consent to Randomization/ Allocation | Reporting Time Period: Randomization/ Allocation through Protocol- Specified Follow- up Period | Reporting Time Period: After the Protocol Specified Follow- up Period | Timeframe to Report Event and Follow-up Information to SPONSOR: |
|-----------------------------------------|-----------------------------------------------------------------------------------------------------------------------------------------------------|-------------------------------------------------------------------------------------------------------------------------|------------------------------------------------------------------------------------------------------------------------|--------------------------------------------------------------------------|
| Non-Serious Adverse Event (NSAE) | Report if: - due to protocol-specified intervention - causes exclusion - participant is receiving placebo run-in or other run-in treatment | Report all from the time of each vaccination through 14 days thereafter. | Not required | Per data entry guidelines |
| Serious Adverse Event (SAE) | Report if: - due to protocol-specified intervention - causes exclusion - participant is receiving placebo run-in or other run-in treatment | Report all for the duration of an individual's study participation. | Report if: - drug/vaccine related. - any death until participant completion of trial (Follow ongoing to outcome) | Within 24 hours of learning of event |
| Pregnancy | Report if: - due to intervention - causes exclusion | Report all – Follow to completion/termination and report outcome | Previously reported – Follow to completion/termination; report outcome | Within 24 hours of learning of event |

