10.4.3 Safety Endpoints

As specified in Section 4, Section 5.4.1.3, and Section 10.6.3, the endpoints that will be used to assess the safety and tolerability of 2-dose and 3-dose regimens of V160 include the following:

- Number of participants experiencing solicited injection site AEs within Days 1 through 5 after each vaccination visit; solicited systemic AEs (including tiredness, muscle pain, headache, and joint pain); and vaccine-related systemic AEs, SAEs, and elevated temperatures within Days 1 through 14 after each vaccination visit
- Incidence of any SAE at any time during the study

- Incidence of vaccine-type viral shedding
- Outcomes of pregnancies.

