10.9.2 Sample Size and Power for Safety Analyses

Testing of hypotheses relating to safety will not be conducted in this study. Thus, power and Type 1 error considerations relating to safety analyses are not applicable in this study.

The probability of observing a specific AE in specific treatment arms of this study depends on the number of vaccinated participants with safety follow-up and the underlying incidence of that specific AE in the study population. In each treatment arm, assuming that all 700 participants randomized into the study will have safety follow-up, then there is a >99% chance of observing at least one specific AE if the incidence of that AE is at least 1 in every 150 participants; >90% chance if the incidence is at least 1 in every 300 participants. If no vaccine-related SAEs are observed among the 700 participants randomized in a specific V160 treatment arm, this study will provide 97.5% confidence that the underlying percentage of participants with vaccine-related SAE is $\leq 0.5\%$ (1 in every 200 participants) among V160 vaccinated participants in that V160 arm. This is based on calculation of a 1-sided 97.5% upper confidence limit of a binomial proportion using the exact binomial method of Clopper and Pearson [Clopper, C. J. and Pearson, E. S. 1934] and was done using PASS 2008. For a sample size of 700 per treatment arm, Table 8 provides the critical split of participants with AEs between V160 and placebo arms for which it will be possible to state with 95% confidence that the risk difference (defined as percent in V160 dose regimen group minus percent in placebo) excludes 0%. For a specific AE, given a sample size of 700 per arm, the minimum total number of participants with AEs for which it is possible to state with 95% confidence that the risk difference excludes 0% is 5. As stated in Section 10.6.3, AEs observed in at least 7 participants (representing 1% of N=700 participants per group) in any vaccination group will be categorized as a Tier 2 event. The 95% CIs of the percentage point differences were calculated using the Miettinen and Nurminen method [Miettinen, O. and Nurminen, M. 1985].

Table 8 Critical Counts of Participants with Adverse Events in V160 and Placebo Arms Resulting in the Lower Bound of 95% CI Estimate of Risk Difference to be >0%

| Observed Count of Participants with Adverse Events | | | Risk Difference [†] (V160 – Placebo) | |

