NOTE: IF A RECHALLENGE IS PLANNED FOR AN ADVERSE EVENT WHICH WAS SERIOUS AND WHICH MAY HAVE BEEN CAUSED BY THE SPONSOR'S PRODUCT, OR IF RE-EXPOSURE TO THE SPONSOR'S PRODUCT POSES ADDITIONAL POTENTIAL SIGNIFICANT RISK TO THE PARTICIPANT THEN THE RECHALLENGE MUST BE APPROVED IN ADVANCE BY THE SPONSOR CLINICAL DIRECTOR, AND IF REQUIRED, THE INSTITUTIONAL REVIEW BOARD/INDEPENDENT ETHICS COMMITTEE.

- **Consistency with Study treatment Profile:** Is the clinical/pathological presentation of the AE consistent with previous knowledge regarding the Sponsor's product or drug class pharmacology or toxicology?
- The assessment of relationship will be reported on the case report forms /worksheets by an investigator who is a qualified physician according to his/her best clinical judgment, including consideration of the above elements.
- Use the following scale of criteria as guidance (not all criteria must be present to be indicative of a Sponsor's product relationship).
 - Yes, there is a reasonable possibility of Sponsor's product relationship: There is evidence of exposure to the Sponsor's product. The temporal sequence of the AE onset relative to the administration of the Sponsor's product is reasonable. The AE is more likely explained by the Sponsor's product than by another cause.
 - No, there is not a reasonable possibility of Sponsor's product relationship: Participant did not receive the Sponsor's product OR temporal sequence of the AE onset relative to administration of the Sponsor's product is not reasonable OR the AE is more likely explained by another cause than the Sponsor's product. (Also entered for a participant with overdose without an associated AE.)
- For each AE/SAE, the investigator must document in the medical notes that he/she has reviewed the AE/SAE and has provided an assessment of causality.
- There may be situations in which an SAE has occurred and the investigator has minimal information to include in the initial report to the Sponsor. However, it is very important that the investigator always make an assessment of causality for every event before the initial transmission of the SAE data to the Sponsor.
- The investigator may change his/her opinion of causality in light of follow-up information and send an SAE follow-up report with the updated causality assessment.
- The causality assessment is one of the criteria used when determining regulatory reporting requirements

Follow-up of AE and SAE

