|------------------------------------------------------|---------------------------------------------------------------------------------------------------------------------------------------------------------------------------------------------------------------------------------------------------------------------------------------------------------------------------------------------------------------------------------------------------------------------------------------------------------------------------------------------------------------------------------------------------------------------------------------------------------------------------------------------------------------------------------------------------------------------------------------------------------------------------------------------------------------------|
| Analysis Populations | Efficacy: Per-Protocol Efficacy (PPE) Safety: All Participants as Treated (APaT) |
| Primary Endpoint(s) | 
 Efficacy: number of participants with CMVi in the V160 3-dose regimen and placebo arms. Safety: number of participants experiencing solicited injection site AEs within Days 1 through 5 after each vaccination visit; solicited systemic AEs and vaccine-related serious AEs within Days 1 through 14 after each vaccination visit. |
| Key Secondary Endpoints | Efficacy: number of participants with CMVi in the V160 2-dose regimen and placebo arms. |
| Statistical Methods for Key Efficacy Analyses | The primary and secondary efficacy hypotheses will be evaluated by calculating the efficacy of V160 compared to placebo with respect to the CMVi endpoint. The p-value for testing the hypothesis that VE>0% as well as estimation of the 95% CI of VE will be based on the exact binomial method proposed by Chan and Bohidar [1]. |

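### The vaccine-related SAE row stops at Day 14 after each dose, so a related SAE from Day 15 onward appears only in outputs that are not split by relatedness

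*Combined protocol and SAP*

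**What the plan says.** **What is analysed.** The safety tables (protocol 10.6.3, Table 5; sSAP 3.6.3, Table 1) have one row for related SAEs: "Vaccine-related serious AEs within Days 1 through 14 after vaccination". The primary safety endpoint in the summaries (protocol 10.1, sSAP 3.1) uses the same window: "vaccine-related serious AEs within Days 1 through 14 after each vaccination visit". The endpoint lists (10.4.3, 3.4.3) give "vaccine-related systemic AEs, SAEs, and elevated temperatures within Days 1 through 14 after each vaccination visit". Whole-study SAEs have two outputs: the Tier 2 row for any SAE, which includes SAEs in infants born to participants, and SAE incidence rates by system organ class. Both are per person-year, and neither is specified by relatedness.

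**What is collected.** Protocol 9.3.1 says that SAEs, whatever their cause, "are reportable throughout the duration of an individual's study participation". Its Table 4 says the same in the SAE row: "Report all for the duration of an individual's study participation". Among the events to be reported even outside the specified period is "A serious adverse event that is considered by an investigator who is a qualified physician to be vaccine related". Appendix 4 sets no time limit on causality: "For each AE/SAE, the investigator must document in the medical notes that he/she has reviewed the AE/SAE and has provided an assessment of causality".

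**Where the window is missing.** The Tier 2 summary panel (10.1, 3.1) lists related AEs, systemic or serious, without a window. So does the precision statement in 10.9.2 and 3.9.2, which begins "If no vaccine-related SAEs are observed among the 700 participants randomized in a specific V160 treatment arm" and concludes with 97.5% confidence that the underlying percentage is at most 0.5%.

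**The concern.** The information needed to count related SAEs over the whole study is already gathered, yet the only related-SAE row uses a small part of it. An SAE that an investigator attributes to V160 in, say, Month 4 or Month 12 is shown among all-cause SAEs, where unrelated events accrued over years, and infant SAEs, dilute it.

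Two things are at stake. The first is visibility: the interim safety summaries for the eDMC (10.7.2, 3.7.2) are built from the same parameter list, so the gap carries over to them. The second is consistency: the 0/700 statement is worded for related SAEs in general, while the row a reader would look to for that zero covers only the days just after each dose.

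**Working it through.** **1. The plan's own figures.** 10.9.2 assumes that all 700 participants in an arm have safety follow-up.
- Upper limit for 0/700 (one-sided 97.5%, Clopper-Pearson): 1 − 0.025^(1/700) = 0.526%, or 1 in 190. This matches the printed 0.5% to one decimal. A limit of exactly 0.500% would need ln(0.025)/ln(0.995) = 735.9, so 736 participants.
- Chance of seeing at least one event: 1 − (1 − 1/150)^700 = 99.1% (stated as above 99%), and 1 − (1 − 1/300)^700 = 90.3% (stated as above 90%).

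**2. Coverage of the windows.** Three doses × 14 days = 42 days. Under the schedule (Days 1, 61 ± 21 and 183 ± 28) the windows cannot overlap: the earliest second dose is on Day 40, the latest is on Day 82, and the earliest third dose is on Day 155. With 18 months of enrolment and a 3-year study, Day 548 (Month 18) and Day 1096 (Month 36) are taken as the range of participation.

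| SAE collection time | 42 days as a share |
|---|---|
| 548 days | 7.7% |
| 731 days | 5.7% |
| 1096 days | 3.8% |

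So about 92% to 96% of SAE collection time lies outside the related-SAE row. A participant who misses a dose has fewer than 42 days.

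**3. What a late event does to the precision statement.** For x participants with an event out of 700, the upper limit is the 0.975 quantile of Beta(x + 1, 700 − x).

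| Related SAEs over the whole study | Upper limit |
|---|---|
| 0 | 0.53% |
| 1 | 0.79% |
| 2 | 1.03% |

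With zero events inside the windows and one outside, the windowed row still reads 0/700, but the limit for related SAEs at any time is 0.79%.

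**4. How masking could look (illustration only).** Suppose 5 related SAEs in a V160 arm and 0 in placebo, all after Day 14. The planned row shows 0 against 0. A count without the window gives a difference of 5/700 = 0.71%, Miettinen-Nurminen 95% CI 0.17% to 1.66% (Table 8 prints 0.1% to 1.7% for this split).

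For the all-cause row, assume mean follow-up of 2.25 years, so 700 × 2.25 = 1,575 person-years per arm, and b background SAEs per arm. The excess is 5/1,575 = 0.32 per 100 person-years. The half-width of a simple Poisson interval is 1.96 × √(2b + 5)/1,575.

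| Assumed background per person-year | b | 95% CI per 100 person-years |
|---|---|---|
| 1% | 16 | −0.44 to 1.07 |
| 2% | 32 | −0.72 to 1.35 |
| 4% | 63 | −1.11 to 1.74 |

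The documents give no background SAE rate and name no interval method for this row. The split, the rates and the interval are therefore assumptions, used only to show the mechanism.

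**The case against.** The case for leaving the plan alone has real substance.

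- **The window is deliberate and labelled.** It stands in the primary endpoint itself, and 5.4.1.3 says the safety timepoints follow the usual peak of AEs after vaccination. A zero would be reported as a Days 1–14 zero. This stands, and it is a good reason to keep the row. It does not explain why attributed SAEs that are collected anyway should have no whole-study count.
- **Late related SAEs are not lost.** A reader might infer that the plan discards them. The documents do not support that. They reach the sponsor within 24 hours and enter the all-cause SAE comparison with its 95% CI and the SAE rates by system organ class. They may also enter the rows for AEs by system organ class or discontinuations. Safety is judged by clinical review, and the endpoint lists are introduced as inclusive, not exhaustive. The row for related systemic AEs has no window in its title, but 10.4.3 and 3.4.3 place those events within Days 1–14 as well.
- **The 0/700 sentence is conditional.** A reader might set the upper limit for five observed events (1.66%) against the stated 0.5% and call the assurance false. That is not like for like: once a related SAE is observed, the condition fails and the sentence makes no claim. The sentence is also planning text, and nothing says that it will be quoted with the results. What stands is narrower: its condition has no window, so the windowed row alone cannot show that it is met.
- **Late related SAEs may be few or none.** Phase 1 had no SAEs, and the causality criteria weigh time since vaccination. This stands and limits the likely effect.

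**Conclusion.** The gap is real and modest. Every definition of the related-SAE endpoint stops at Day 14 after a dose, while SAE and causality collection runs throughout participation, so no specified row counts related SAEs from Day 15 onward. The windows cover about 4% to 8% of collection time, assuming all three doses and 548 to 1096 days of participation. One late related SAE would move the whole-study upper limit from 0.53% to 0.79%.

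The documents do not support saying that the trial would report a false zero or hide attributed events. They show an incomplete tabulation, together with unwindowed wording in the summary panel and the precision statement that does not match the windowed row. No safety hypothesis is tested, so no error rate or power figure changes. This is a cheap improvement.

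**What to change.** 1. Keep the Days 1–14 row. Add a Tier 2 row to protocol Table 5 and sSAP Table 1, and a matching line in 10.4.3 and 3.4.3, for vaccine-related SAEs at any time in the study.
2. Report it by arm as participants with events and as incidence per person-year, with a 95% CI versus placebo. This follows the plan's own rule, which exempts whole-study SAEs from percentages (10.6.3, 3.6.3). Name the interval method, since the plan names none for person-year comparisons in safety. A Miettinen-Nurminen percentage difference could be added as a supplement, provided that the exemption is reworded to allow it.
3. In 10.9.2 and 3.9.2, state that the 0/700 assurance refers to the any-time count, or else limit the sentence to Days 1–14. Align the Tier 2 summary panel in 10.1 and 3.1.

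The cost is one table row and matching wording in both documents. It needs no new data and leaves SAE collection, hypotheses and type 1 error as they are. The downside is that the reported related-SAE count may be slightly less favourable.
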